### **3.2 Benefits and Risks**

In Phase 1 and Phase 2 studies of risankizumab in patients with psoriasis, the majority of subjects receiving risankizumab achieved 90% improvement of their disease and risankizumab was well tolerated.

As with many immune modulating agents, risankizumab may impair immune function resulting in a risk of infection. This will be monitored by collection of all AEs during the treatment and observation periods.

Subjects with active infection will not be included in the study.

Subjects with a positive QuantiFERON®-test or a positive Purified Protein Derivative (PPD) skin test for tuberculosis (TB) must fulfill entry criteria as specified in Section 5.2.1 of this protocol. Interleukin-23 inhibition is not known to increase the risk of TB infection or impair the response to TB infection in animal models. Thus, low

risk subjects with positive Quantiferon testing do not need to be treated with anti-tuberculosis therapy prior to receiving risankizumab, but should be carefully monitored for any sign of TB reactivation. Absence of TB reactivation, despite not receiving anti-tuberculosis prophylaxis will provide important information in humans as to whether TB testing is required prior to treatment with risankizumab.

There is not enough information at this time to rule out a risk of cancer with risankizumab, but this risk is considered small with this type of compound as experience with the anti-IL-12/23 mAb ustekinumab has not suggested significant risk for cancer or serious infection.

Increases in major adverse cardiovascular (MACE) events including myocardial infarction, cerebrovascular accident, and cardiovascular death, reported initially with anti-IL-12/23 agents, such as ustekinumab, have not been observed in longer term studies. Although rare, a potential for drug-induced liver injury (DILI) is under constant surveillance by sponsors and regulators. Therefore, this study requires timely detection, evaluation, and follow-up of laboratory alterations in selected liver laboratory parameters to ensure subjects' safety.

In conclusion, the benefit-risk profile of risankizumab is considered appropriate for this stage of clinical development.

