### **5.3.1.1            Study Procedures**

Study procedures will be performed at the study visits as specified in [Appendix C](#). Study visits are scheduled at Week 0/Day 1, Weeks 4, 8, 12, 16, 20 and 24/ET. Study procedures are discussed in detail in this section, with the exception of drug concentration measurements and antibody measurements (discussed in Section [5.3.2](#)), study drug administration (discussed in Section [5.5.1](#)), and the collection of AE information (discussed in Section [6.1.1.1](#)). All study data will be recorded in source documents and on the appropriate eCRFs.

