### **Clinical Laboratory Tests**

Blood samples will be obtained for the laboratory tests listed ("complete lab") in [Table 3](#) at Screening, Week 0, 8, 16 and 24 visits. At Week 4, 12, 20 visits only "targeted lab," i.e., CBC with differential count (hematology), ALT, AST, gamma-GT, alkaline phosphatase (AP) and serum creatinine, will be obtained. Blood draws should be performed after all clinical assessments and patient reported outcomes, ECGs, and vital sign determinations are obtained before study drug administration during a visit.

Urine samples will be obtained for urinalysis testing at all visits as listed in [Table 3](#). The central laboratory will be responsible for performing a macroscopic urinalysis (urine

dipstick) on the collected urine specimens. Specified abnormal macroscopic urinalyses will be followed up with a microscopic analysis at the central laboratory.

A certified central laboratory will be utilized to process and provide results for the clinical laboratory tests. All abnormal laboratory tests that are considered clinically significant by the investigator will be followed to a satisfactory resolution. Laboratory abnormalities are considered to be adverse events only if they result in discontinuation from the study, necessitate therapeutic medical intervention, and/or if the Investigator considers them to be an adverse event.

Instructions regarding the collection, processing and shipping of these samples will be provided by the central laboratory chosen for this study.

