### **5.4 Removal of Subjects from Therapy or Assessment**

#### **5.4.1 Discontinuation of Individual Subjects for Either Risankizumab or FUMADERM®**

A subject may withdraw from the study at any time. The Investigator may discontinue any subject's participation for any reason, including an adverse event, safety concerns or failure to comply with the protocol.

Whether randomized to risankizumab or to FUMADERM®, subjects will be withdrawn from the study immediately if any of the following occur:

1. Clinically significant abnormal laboratory results or adverse events, which rule out continuation of study drug, as determined by the Investigator and the AbbVie TA MD.
2. The Investigator believes it is in the best interest of the subject.
3. The subject requests withdrawal from the study.
4. Deviation from inclusion and exclusion criteria was noted after the subject started study drug, when continuation of the study drug would place the subject at risk as determined by the AbbVie TA MD.
5. Introduction of prohibited medications or dosages when continuation of the study drug would place the subject at risk as determined by the AbbVie TA MD.
6. Subject is non-compliant with TB prophylaxis (if applicable) or develops active TB at any time during the study.
7. The subject becomes pregnant while on study drug.
8. Subject has known malignancy, except for localized non-melanoma skin cancer. Discontinuation for carcinoma in-situ of the cervix is at the discretion of the Investigator.
9. Subject is significantly non-compliant with study procedures which would put the subject at risk for continued participation in the study in consultation with the AbbVie TA MD.
10. Occurrence of following hepatic test abnormalities considered by the investigator to be related to study drug:
  - Confirmed ALT or AST  $> 8 \times$  Upper Limit of Normal (ULN)
  - Confirmed ALT or AST  $> 5 \times$  ULN for more than 2 weeks
  - Confirmed ALT or AST  $> 3 \times$  ULN and (total bilirubin  $> 2 \times$  ULN)
  - Confirmed ALT or AST  $> 3 \times$  ULN with the appearance of fatigue, nausea, vomiting, right upper quadrant pain or tenderness, fever, rash, and/or eosinophilia ( $> 5\%$ )

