### **Hepatic Adverse Events**

In the case of any of the following AEs, a Hepatic Adverse Event eCRF should be completed:

- Discontinuation or interruption of study drug due to a hepatic related AE
- A hepatic related SAE
- A subject experiencing an ALT/AST  $> 8 \times$  ULN
- A subject experiencing an ALT/AST  $> 3 \times$  ULN in conjunction with a total bilirubin  $> 2 \times$  ULN.

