- b. Subjects that discontinue the study prior to the end of the study will have a follow-up phone call within 15 weeks after the last dose of FUMADERM® provided as study medication for collection of safety data. Subjects that elect to enroll into a separate extension study will not require the Week 31 Follow-Up phone call as part of this trial.
- c. Update history.
- d. Serum pregnancy test in all women at screening and if the urine pregnancy test is positive at any other visit. Urine pregnancy tests are to be performed in all women of child bearing potential prior to administration of study drug at all dosing visits.
- e. Height and weight will be measured at the Screening Visit only (with shoes off).
- f. Targeted laboratory samples should be limited to CBC with differential count (hematology), serum creatinine (substrates) and ALT, AST, gamma-GT and AP (enzymes).
- g. (FSH) To be done at Screening in all women aged ≤ 55 years with no menses for 12 or more months without an alternative medical cause.
- h. Infection screening consists of Hepatitis B Surface Antigen (qualitative), Hepatitis B Surface Antibody (qualitative), Total Hepatitis B Core Antibodies (qualitative), Hepatitis B Virus DNA (quantitative) reflex, Hepatitis C Virus RNA (quantitative) reflex, HIV-1 and HIV-2 Antibody (qualitative), PPD/QuantiFERON-TB.
- i. For FUMADERM® INITIAL and FUMADERM® provided as study medication only.
- j. Prior to other procedures.
- k. SC risankizumab 150 mg at Week 0/Day 1, Week 4 and Week 16. Risankizumab will be administered at the study site by authorized site personnel (e.g., study nurse) after all study procedures have been completed.
- l. Oral FUMADERM® daily starting at Week 0/Day 1 and until Week 24 (the last dose will be in the morning of the day of Week 24 visit). FUMADERM® INITIAL starting at Week 0/Day 1 until Week 2 and FUMADERM® starting at Week 3, both at starting dose of 1 tablet per day, followed by a dose increase of one tablet per week, depending on efficacy response and tolerability. The maximum dose of FUMADERM® of 6 tablets per day should not be exceeded.
- m. PK and ADA samples are collected only from the subjects receiving risankizumab.

---

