### Liver Function Tests

Additional summaries will be presented for liver function tests including ALT or serum glutamic-pyruvic transaminase (SGPT), AST or serum glutamic-oxaloacetic transaminase (SGOT), alkaline phosphatase, and total bilirubin. Each laboratory value will be categorized as follows:

- $< 1.5 \times \text{ULN}$
- $\geq 1.5 \times \text{ULN} - < 3.0 \times \text{ULN}$
- $\geq 3.0 \times \text{ULN} - < 5.0 \times \text{ULN}$
- $\geq 5.0 \times \text{ULN} - < 10.0 \times \text{ULN}$
- $\geq 10.0 \times \text{ULN} - < 20.0 \times \text{ULN}$

---

- $\geq 20.0 \times \text{ULN}$

Shift tables of Baseline to the maximum (relative to the normal range, i.e., the largest multiple relative to the upper limit of normal) values, and from Baseline to final value will be presented using these categories. A listing of potentially clinically important liver function laboratory values will be provided. The listing will include all subjects who met any of the following four criteria:

- $\text{ALT} \geq 3 \times \text{ULN}$ , or
- $\text{AST} \geq 3 \times \text{ULN}$ , or
- Alkaline phosphatase  $\geq 1.5 \times \text{ULN}$ , or
- Total bilirubin  $\geq 2 \times \text{ULN}$ .

A listing of possible Hy's Law cases, defined as those who meet all of the following conditions will be provided:

- $\text{ALT} > 3 \times \text{ULN}$  or  $\text{AST} > 3 \times \text{ULN}$
- Associated with an increase in bilirubin  $\geq 2 \times \text{ULN}$
- Alkaline phosphatase  $< 2 \times \text{ULN}$ .

In addition, a graphical summary highlighting potential cases of Hy's Law within each treatment group will be presented. The maximum on-treatment values of total bilirubin and ALT will be plotted each on a scale as multiples of the upper limit of normal. The figure will show areas that meet the criteria of cholestasis (total bilirubin  $> 2 \times \text{ULN}$ ), Temple's corollary ( $\text{ALT} > 3 \times \text{ULN}$ ) and Hy's Law as the combination of these two factors.

All analyses will be conducted in the Safety Population.

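### No total bilirubin is scheduled at Weeks 4, 12 and 20, so the bilirubin-dependent hepatic criteria cannot be assessed from scheduled tests at 3 of 6 post-baseline visits

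*Protocol*

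**What the plan says.** **Visits and panels.** Protocol 5.3.1.1 states: "Study visits are scheduled at Week 0/Day 1, Weeks 4, 8, 12, 16, 20 and 24/ET". The complete laboratory panel is drawn "at Screening, Week 0, 8, 16 and 24 visits". At Weeks 4, 12 and 20 only the targeted panel is taken: "CBC with differential count (hematology), ALT, AST, gamma-GT, alkaline phosphatase (AP) and serum creatinine, will be obtained". Footnote f of Appendix C makes the same list a ceiling: "Targeted laboratory samples should be limited to CBC with differential count (hematology), serum creatinine (substrates) and ALT, AST, gamma-GT and AP (enzymes". Protocol Table 3 lists total bilirubin under substrates, so it belongs to the complete panel only. The SAP follows this split. The targeted analytes have windows at every visit (SAP Table 1), and the remaining analytes have windows at Weeks 8, 16 and 24 only (SAP Table 3).

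**Where bilirubin is needed.**
- Protocol 5.4.1, item 10, withdraws a subject on "Occurrence of following hepatic test abnormalities considered by the investigator to be related to study drug". Four alternative limbs follow, and the third combines confirmed ALT or AST above 3 × ULN with total bilirubin above 2 × ULN.
- Protocol 6.1.1.3 asks for a hepatic eCRF in four situations, one of which is ALT/AST above 3 × "ULN in conjunction with a total bilirubin" above 2 × ULN.
- SAP 11.3.2 (Liver Function Tests) lists possible Hy's Law cases from ALT or AST, bilirubin and alkaline phosphatase together. It also provides a figure: "The maximum on-treatment values of total bilirubin and ALT will be plotted each on a scale as multiples of the upper limit of normal".

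**Stated aim.** Protocol 3.2 says of drug-induced liver injury that "this study requires timely detection, evaluation, and follow-up of laboratory alterations in selected liver laboratory parameters".

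**The concern.** The enzymes are measured every 4 weeks and bilirubin every 8, yet several safety provisions depend on the two together. A concurrent rise at Week 4, 12 or 20 would reach the investigator as an enzyme rise alone. The bilirubin limb and its eCRF trigger would then have no value to act on unless the site ordered the test on its own initiative.

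The Hy's Law listing has the same gap: the targeted panel already supplies ALT, AST and alkaline phosphatase, and bilirubin is the one missing input. A short-lived bilirubin peak at these visits would be absent from the listing and would understate the plotted maximum, in either arm.

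The first interval without a scheduled bilirubin runs from Week 0 to Week 8. That spans the whole pre-specified FUMADERM® step-up in protocol Table 5 and the second risankizumab dose at Week 4.

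**Working it through.** The plan gives no figure to reproduce. The check is a count of visits against criteria.

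**Step 1. Visits.** Post-baseline clinic visits are Weeks 4, 8, 12, 16, 20 and 24/ET, so 6. Those with the complete panel are Weeks 8, 16 and 24, so 3. Those with only the targeted panel are Weeks 4, 12 and 20, so 3. Share without a scheduled bilirubin: 3/6 = 50%. The Week 31 contact is a phone call and is not counted.

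**Step 2. Sampling interval.** Bilirubin at Weeks 0, 8, 16 and 24 gives gaps of 8, 8 and 8 weeks. ALT/AST at Weeks 0, 4, 8, 12, 16, 20 and 24 gives six gaps of 4 weeks. From a targeted visit to the next complete panel is 28 nominal days. With the ±4-day visit window on both visits, the range is 28 − 8 = 20 to 28 + 8 = 36 days.

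**Step 3. Limbs of item 10 against the targeted panel.**

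| Limb (confirmed ALT or AST) | Further input | Laboratory input in targeted panel? |
|---|---|---|
| > 8 × ULN | none | yes |
| > 5 × ULN for more than 2 weeks | duration | yes |
| > 3 × ULN | total bilirubin > 2 × ULN | **no** |
| > 3 × ULN | symptoms and/or eosinophilia > 5% | yes (differential count) |

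Limb-by-visit checks: 4 × 6 = 24. Checks lacking a scheduled laboratory input: 1 × 3 = 3, or 3/24 = 12.5%. The other 21 have theirs. With bilirubin at all six visits the count falls from 3 to 0.

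**Step 4. Does other text supply the missing value?** The text after protocol Table 3 requires clinically relevant abnormal results to be confirmed and repeated. That covers the test that was abnormal; it does not call for one that was not run. Table 3 and its notes do write out conditional tests where they are wanted: CK-MB when CK is raised, direct and indirect bilirubin when total is raised, and viral DNA or RNA after serology. None links a raised ALT or AST to bilirubin. Urine bilirubin is on the dipstick at every visit, but it is not the serum multiple of ULN that the criteria use.

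**Step 5. SAP windows.** Under SAP Table 3 a bilirubin from Day 29 or Day 85 falls in the Week 8 window (Days 2 to 85, target 57), and one from Day 141 falls in the Week 16 window (Days 86 to 141, target 113). Each is 28 days from its target. SAP 6.0 keeps the assessment closest to target. Extra values would therefore drop out of the by-visit summaries whenever the regular value is closer, unless the windows change too.

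**The case against.** The strongest reply is that the schedule sets routine panels while the withdrawal criterion acts on whatever confirmed results exist. Every limb requires a confirmed ALT or AST, so none is meant to fire on a single scheduled draw, even at Week 8, 16 or 24. A raised ALT at Week 12 should lead to unscheduled testing, at which bilirubin may well be drawn. Items 1 and 2 of 5.4.1 also allow withdrawal without any bilirubin value, and a subject who stops early has the Week 24/ET panel within 2 weeks of that decision.

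Most of this stands, and it rules out three stronger readings that a reader might infer:

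- *The hepatic withdrawal rule cannot be evaluated at half the visits.* Not so: this applies to one limb in four.
- *The panel and the rule contradict each other.* The documents do not tie the rule to scheduled tests or require it to be evaluated at every visit. The passages are not aligned, which is a weaker statement.
- *The Hy's Law outputs cannot be produced.* The figure uses each subject's separate maxima, and the listing sets no time window for the bilirubin rise, so values from different visits can be paired.

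What the reply does not remove is that bilirubin at the confirmatory draw is possible but nowhere required. Protocol 3.2 also describes raised liver function tests with FUMADERM® as among the uncommon to very rare events, so few cases are to be expected. That limits the size of the problem without closing the gap.

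**Conclusion.** The point holds in a limited form. At Weeks 4, 12 and 20, one of four withdrawal limbs, one of four hepatic eCRF triggers and a same-visit Hy's Law check lack a scheduled serum bilirubin. The consequence is reduced sensitivity to a transient concurrent rise, with a wait of about 4 weeks for the next scheduled value if no unscheduled test is done.

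This rests on two readings of the documents: that the confirm-and-repeat provision does not itself mandate bilirubin, and that total bilirubin is drawn only with the complete panel. The documents give no rate of concurrent elevation, so the number of subjects affected cannot be estimated and may be zero. The case for changing the plan is its own stated aim of timely detection, set against a very small cost.

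**What to change.** Reconcile protocol 5.3.1.1 and Appendix C footnote f with 5.4.1 item 10, 6.1.1.3 and SAP 11.3.2. The sponsor should state at which visits the combined criteria are meant to apply, and make total bilirubin available from the blood already drawn at those visits. The withdrawal criteria and all thresholds stay as they are, and no new trigger level is proposed.

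If bilirubin is added at Weeks 4, 12 and 20, SAP Tables 1 and 3 should follow, moving total bilirubin to the visit windows used for ALT and AST so that the new values enter the by-visit summaries.

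Cost: at most 110 subjects × 3 visits = 330 extra analyte results, a revised central-laboratory panel and matching text edits. No new visit or tube is needed.

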**Table 3. Clinical Laboratory Tests**

Category	Test Name
Hematology	Hematocrit (Hct) Hemoglobin (Hb) Red Blood Cell Count/Erythrocytes White Blood Cells/Leukocytes Platelet Count/Thrombocytes
Diff. Automatic	Neutrophils (absolute count) Eosinophils (absolute count) Basophils (absolute count) Monocytes (absolute count) Lymphocytes (absolute count)
Diff. Manual (if Diff Automatic is abnormal)	Neutrophils, bands (Stabs) Neutrophils, polymorphonuclear (PMN) Eosinophils Basophils Monocytes Lymphocytes
Enzymes	AST(GOT) ALT(GPT) Alkaline Phosphatase (AP) Creatine Kinase (CK) CK-MB, only if CK is elevated Gamma-glutamyl transferase (GGT/γ-GT)
Electrolytes	Calcium Sodium Potassium Chloride Bicarbonate
Substrates	Glucose BUN Creatinine Bilirubin Total Bilirubin Direct (if total is elevated) Bilirubin Indirect (if total is elevated) Albumin C-Reactive Protein (CRP) (high sensitivity) Cholesterol, total a Triglycerides a LDL-Cholesterol a HDL-Cholesterol a FSH b

**Table 3. Clinical Laboratory Tests (Continued)**

Category	Test Name
Urine Pregnancy test (only for female subjects of childbearing potential) c	Human Chorionic Gonadotropin in the urine
Serum Pregnancy test (in all female subjects at screening or if urine pregnancy test is positive in female subjects of child bearing potential)	Human Serum Chorionic Gonadotropin
Autoantibodies (only at screening)	Rheumatoid Factor
Urinalysis (dipstick)	Urine Nitrite Urine Protein Urine Glucose Urine Ketone Urobilinogen Urine Bilirubin Urine RBC/Erythrocytes Urine WBC/Leukocytes Urine pH Urine creatinine
Urine-Sediment (microscopic examination, only if urine analysis abnormal)	Urine Sediment Bacteria Urine Cast in Sediment Urine Squamous Epithelial Cells Urine Sed. Crys., Unspecified Urine Sediment RBC/Erythrocytes Urine Sediment WBC/Leucocytes
Urine	UACR
Infection screening	Hepatitis B Surface Antigen (qualitative) d,e Hepatitis B Surface Antibody (qualitative) d,e Hepatitis B Core Antibodies total (qualitative) d,e Hepatitis B Virus DNA (quantitative) d,e Hepatitis C Antibodies (qualitative) d,e Hepatitis C Virus RNA (quantitative) d,e HIV-1, and HIV-2 Antibody (qualitative) d,e QuantiFERON ® -TB (if applicable)

- a. To be done at screening only.
- b. (FSH) To be done at Screening in all women aged  $\leq 55$  years with no menses for 12 or more months without an alternative medical cause.
- c. Urine pregnancy test performed at every visit except Screening.
- d. Hepatitis B, Hepatitis C and HIV testing will be performed at screening.
- e. If Hepatitis B Surface Antigen is negative but Hepatitis B Core Antibodies total is positive and/or Hepatitis B Surface Antibody is positive, Hepatitis B Virus DNA will be quantified. If Hepatitis B Virus DNA level is undetectable at screening, the subject can participate in this study. If Hepatitis C Virus Antibodies is positive, Hepatitis C Virus RNA will be quantified. If Hepatitis C RNA level is undetectable at screening, the subject can participate in this study.

Clinically relevant abnormal findings will be reported as baseline conditions or AEs. A clinically relevant value may be either in- or outside the reference range. Clinically relevant abnormal laboratory test results must be confirmed and should be repeated until normalization or stabilization or until an alternative explanation has been found.

### **Clinical Assessments and Patient Reported Outcomes**

Clinical and patient reported efficacy endpoints will be assessed over the course of the study at the time points defined in [Appendix C](#). Patient reported outcomes (PROs) should be completed by the patient on his/her own in a pre-specified order in a quiet area/room before any other visit assessments or treatments, and, if possible, before any interaction with the investigator or other members of the study team. Details of the following clinical and efficacy assessments are listed in the appendices. Details of the patient reported outcomes are listed below.

#### Clinical Assessments

- PASI
- BSA
- sPGA
- PPASI
- PSSI
- NAPPA-CLIN

#### Patient Reported Outcomes

The order of completion should be as follows, applicable for each PRO as specified in [Appendix C](#).

- PSS
- DLQI
- SF36
- PBI

- HADS
- PtGA
- EQ-5D-5L

### **Psoriasis Symptom Scale (PSS)**

The PSS is a four-item PRO instrument that assesses the severity of psoriasis symptoms in patients with moderate to severe psoriasis. The symptoms included are: pain, redness, itching and burning from psoriasis. Current symptom severity is assessed as a daily diary, using a 5-point Likert-type scale ranging from 0 (none) to 4 (very severe).

